8.2 Sample Size and Power Calculation

Assuming the true rate for freedom from documented symptomatic AF, AT, or AFL episodes through 12-months follow-up is about 65% with CF-guided approach and a historic control performance goal of 50%,¹² a sample size of 150 is needed in order to have 95% power to have the lower bound of the two-sided 95% confidence interval of this recurrence free rate above the historic control performance goal. This sample size is computed using nQuery Advisor® version 7.0. Considering 20% dropout rate, a sample size of 188 is needed. This study will enroll approximately 200 subjects (no less than 188).

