6.4 Ablation Parameters

Descriptive analysis is conducted for ablation procedure parameters, and the procedure parameters include:

- Total X-ray fluoroscopy dose (mGr)
- Intraoperative transcatheter fluid infusion (ml)
- The maximum infusion rate of the intraoperative transcatheter fluid (ml/min)
- Whether the subject has been observed for 30 minutes after CPVI
- Whether isoproterenol has been given to induce fibrillation atrial 30 minutes after CPVI
- Whether other drugs have been given to induce fibrillation atrial 30 minutes after CPVI
- Whether an immediate success has been achieved
- Whether the exit block has been observed
- Presence of linear ablation
- Presence of other ablation
- Whether the sheathing canal has been used during the procedure
- Whether CART03 version 3.2 or later version has been used to mapping the left atrium before radiofrequency ablation
- Whether the VisiTag module has been used
- Whether radiofrequency discharge is conducted
- Average power (watt)
- Average temperature (C)
- CF
- Number of PV reconnection targets
- Procedual time, ablation time and fluoroscopy time
- The longest duration of one-time single discharge (second)
- The maximum decrease in impedance value (ohm)
- Presence of any other types of spontaneous arrhythmia during the procedure

- Presence of any other types of induced arrhythmia during the procedure

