6.5 Effectiveness Analysis

6.5.1 Primary Efficacy Endpoint Analysis

ITT population is used for the main analysis of the primary endpoint, and PP population is used for supportive analysis.

The primary endpoint for this study is freedom from documented symptomatic AF, AT, or AFL episodes through 12-months follow-up after the index ablation procedure (includes a 3 months blanking period).

The following will also be considered primary effectiveness failures and will be included in the effectiveness analysis population:

- Acute procedural failure (i.e., failure to confirm entrance block in all pulmonary veins with an isoproterenol intravenous challenge 0.5 h post procedure or use of a non-study catheter to treat the study arrhythmia);
- A repeated ablation after the 90-day blanking period

Atrial tachyarrhythmia recurrence events will be recorded and included in study analysis after a 90-day blanking period. Recurrence during the blanking will not be considered treatment failure.

The number of subjects who achieved this endpoint and its percentage will be presented. A two-sided binomial exact 95% confidence interval will be computed. Superiority against historic control performance goal (50%) after applying THERMOCOOL® SMARTTOUCH™ catheter with contact sensitivity will be claimed if the lower bound of this confidence interval is above 50%.

For the subjects failing to be followed up to the primary endpoint, with conservative consideration, these subjects are considered as primary effectiveness endpoint failure in the main analysis.

Sensitivity analysis will be conducted for the primary endpoints using the methods below:

- For the subjects failed to be followed up to the primary endpoint, the primary endpoint is considered as missing in the analysis, and the subjects will be excluded from ITT analysis set.

A Kaplan-Meier analysis will be performed for the time to the first documented symptomatic AF, AT, or AFL episode. The first quartile, median, third quartile and 95% confidence intervals of the first quartile, median and the third quartile will be computed.

Kaplan-Meier curves for episode time of symptomatic AF, AT or AFL first recorded during 12 months follow-up (Day 91 to 361) after the first ablation will be presented.

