Logistic regression method will be used to analyze the effect of baseline variables and procedure parameters on the primary effectiveness endpoint. For the influence factor of episode rate, univariate logistic regression analysis model will be first used for preliminary screening of influence factors, of which, the influence factor with p-value <0.2 will be placed into multiple factor regression model for further analysis; and step-wise regression method will be used for further variable screening, of which, the influence factor with p-value <0.2 will be removed from multiple factor model. Please refer to baseline characteristics in Section 6.3.3.

Repeat ablation beyond the blanking period will be described and summarized.

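### SAP 6.5.1 builds its exploratory recurrence model by a p<0.2 screen and stepwise selection on an open list, so chance alone will probably put spurious predictors in it

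*SAP*

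**What the plan says.** SAP 6.5.1 relates baseline variables and procedure parameters to the primary effectiveness endpoint by logistic regression. Each candidate is first tested alone; then "the influence factor with p-value <0.2 will be placed into multiple factor regression model for further analysis". Stepwise regression follows for further screening. As printed, that step removes factors whose p-value is below 0.2.

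For candidates the paragraph says only "Please refer to baseline characteristics in Section 6.3.3". Procedure parameters are mentioned without a cross-reference; the one list of them is in SAP 6.4, introduced by "Descriptive analysis is conducted for ablation procedure parameters, and the procedure parameters include". The paragraph sets no limit on model size and gives no shrinkage, internal validation or multiplicity control. It does not say that odds ratios or confidence intervals will be reported for this model, although SAP 6.1 says in general terms that two-sided 95% intervals will be presented.

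Protocol 8.4.2 describes the covariate work as exploration. The confirmatory claim rests on a different calculation, the success proportion against 50%: "A two-sided binomial exact 95% confidence interval will be computed".

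**The concern.** This is the only multivariable analysis of recurrence whose method the SAP spells out. Filtering many candidates by their p-values and then refitting the survivors to the same data keeps those whose estimates happen to lie far from zero. The p-values from the final model, and any intervals, are computed as if that model had been fixed in advance. With few failures per candidate, readers will probably be given predictors that are noise, with nothing in the output to show it.

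The open list brings a second fault. SAP 6.4 includes whether immediate success was achieved. Under SAP 4.2.1 and 6.5.1 an acute failure is a primary failure by definition, so this variable is part of the outcome. Offered as a predictor, it gives an empty cell (no acute failure can be a success) and an ordinary logistic model cannot estimate its odds ratio.

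**Working it through.** **The plan's own figure.** Protocol 8.2 assumes that the true success rate "is about 65% with CF-guided approach and a historic control performance goal of 50" per cent, and states that "a sample size of 150 is needed in order to have 95% power". With the exact interval at n = 150, at least 88 successes are needed for a lower bound above 50%; the one-sided error is 0.0204 and power at 65% is 0.955. Then 150 / (1 - 0.2) = 187.5, so 188, as stated ("Considering 20% dropout rate, a sample size of 188 is needed"). The sample size reproduces. The plan gives no figure for the logistic model.

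**Candidates.** SAP 6.3.3 has 7 + 11 + 7 + 5 + 5 + 1 + 2 = 38 bullets, plus age, gender and nationality = 41. SAP 6.4 has 23 bullets, or 25 variables when the three times are split. The total is 38 + 23 = 61, or 41 + 25 = 66. That is a ceiling. Some items can hardly vary under the entry and procedure rules (atrial thrombus, CARTO version, VisiTag use, RF discharge), and several type items are nested in presence items. I take 30 to 40 usable candidates as an assumption.

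**Failures** (35% failure rate; enrolment 188 to 200; 20% loss):
- No losses: 0.35 x 188 = 66 (70 at 200).
- Losses counted as failures, as in the main analysis of SAP 6.5.1: 0.2 x 188 + 0.35 x 0.8 x 188 = 90 (96 at 200).
- Losses excluded, as in the sensitivity analysis: 0.35 x 0.8 x 188 = 53 (56 at 200).

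Failures per candidate run from 53/66 = 0.8 to 96/30 = 3.2.

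**False predictors.** As a rough guide, the chance that at least one of k independent null candidates has p<0.05 when each is tested once is 1 - 0.95^k: 79% for k = 30, 87% for 40, 95% for 60. The stated algorithm was then simulated: all candidates null, half binary at 30% prevalence and half continuous, univariate p<0.2 screen, backward removal of p>=0.2, 400 runs per row (Monte Carlo standard error about 2 points at 81%).

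| Candidates | N / failures | Correlation | Pass screen | Final model | With p<0.05 | Runs with at least one p<0.05 |
|---|---|---|---|---|---|---|
| 30 | 188 / 66 | 0 | 6.1 | 5.0 | 1.8 | 81% |
| 40 | 188 / 66 | 0 | 8.2 | 6.6 | 2.4 | 88% |
| 60 | 188 / 66 | 0 | 11.9 | 9.1 | 3.8 | 97.5% |
| 60 | 188 / 91 | 0 | 12.1 | 9.2 | 3.9 | 98% |
| 60 | 150 / 53 | 0 | 12.2 | 8.9 | 3.9 | 97.5% |
| 60 | 188 / 66 | 0.3 | 12.1 | 5.5 | 2.6 | 88% |

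A second simulation with independent null candidates and 53 to 90 failures gave 62-69% with 20 candidates, 82-91% with 30 to 40 and 96-97% with 60. A single unpenalised model with six fixed factors gave 27%, in line with 1 - 0.95^6 = 26%.

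**Intervals.** Standard errors of retained factors were 1.10 to 1.23 times the univariate ones, so widths are not small. Nominal 95% intervals of retained null factors covered the truth 53-64% of the time, but under a global null this only restates the false-positive share (1 - 3.83/9.1 = 58%) and is not a further harm.

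**Removal rule as printed.** Dropping factors with p<0.2 left about 2 factors in the 60-candidate case, none with p<0.05.

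**The case against.** The strongest reply is that the analysis is exploratory and decides nothing: it feeds neither the sample size nor the performance-goal test, and contact force has its own named comparison in SAP 6.5.3. That stands, and it limits the seriousness. It does not justify a procedure that names at least one false factor in most null runs when a short fixed model is available.

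Second, the candidate pool is a count of descriptive lists, and the programming specifications and mock tables (SAP 10 and 11) are separate documents that may narrow it. This also stands, so 61 to 66 is a ceiling. At 30 to 40 candidates, however, the rate is still 80-90%. Correlation helps somewhat: 88% rather than 97.5% at 60 candidates.

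Three stronger readings are tempting, and the documents do not support them:
- A reader might infer that the confidence intervals will be far too narrow. Their widths are near normal. The fault is that selected estimates are pushed away from zero, and SAP 6.5.1 promises no intervals for this model.
- A reader might infer that the text as printed produces the false predictors. Taken literally, the removal rule leaves nothing significant; the harm follows only if that sentence is a slip for the usual rule.
- A reader might set 66 failures against some 60 candidates and conclude one each. That overlooks the SAP's rule that losses count as failures, which gives 90 to 96 at the planned 20% loss.

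**Conclusion.** The point holds as a defect in an exploratory analysis that should be corrected. With the removal rule read the usual way round, the algorithm would report at least one false p<0.05 in about 80-90% of runs with 30 to 40 independent null candidates, and in 96% or more with 60. The number of failures, from 53 to about 90, hardly changes this. The result assumes that no candidate has a real effect and that candidates are independent; real effects or correlation would change the counts, but the reported p-values would still ignore the selection. Immediate success should not be a candidate in any case. A reader might suppose that the 50% performance-goal conclusion is weakened; it is not, because that conclusion uses only the exact interval for the success proportion.

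**What to change.** In SAP 6.5.1, replace the univariate screen and stepwise selection by one model:

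- Name the factors before database lock, from items already collected, at about 10 failures per factor: 53/10 to 96/10, so roughly 5 to 9. State which outcome set the model uses (losses as failures, or losses excluded), since that fixes the number. Age, sex, AF history, left atrial diameter, LVEF and average CF would be one possible list.
- Exclude process flags (for example, whether left atrial diameter was tested) and endpoint components, immediate success in particular.
- Fit the model once by Firth logistic regression and report every odds ratio with its 95% interval, whatever the p-value. Ridge is less suitable because it has no standard confidence intervals.
- Label the results exploratory, and show the remaining variables by outcome descriptively, without p-values.

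If any stepwise step is kept, the direction of its removal rule must be corrected.

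The cost is SAP wording only; no new data are needed. The downside is that factors off the list get no adjusted estimate. Even the short model is not free of chance findings: six fixed factors fitted without penalisation still give about 27% under the null, which is why the exploratory label matters.

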8.4.3 Secondary Endpoints

For acute success rate, the number of subjects who achieved this endpoint and its percentage will be presented. A two-sided binomial exact 95% confidence interval will be computed.

For CF and Force Time Integral for index procedure by PV segments, descriptive summary statistics and 95% two-sided asymptotic confidence intervals will be presented.

For number of PV reconnection after the index procedure, descriptive summary statistics and 95% two-sided asymptotic confidence intervals will be presented. Percentage of PV reconnection after the index procedure will be computed for each subject. And then the descriptive summary statistics and 95% two-sided asymptotic confidence intervals will be used to summarize the percentage of PV reconnection across subjects. Frequency counts and percentages will be used to summarize the sites of PV reconnection after the index procedure.

For total procedural, ablation time and fluoroscopy time, descriptive summary statistics and 95% two-sided asymptotic confidence intervals will be presented.

Correlation between the secondary efficacy endpoints and the primary efficacy endpoint will be explored.

Adverse events observed during the study will be coded by Medical Dictionary for Regulatory Activities Medications (MedDRA). Adverse events will be summarized by System Organ Class (SOC) and Preferred Term (PT) using counts and percentages. Additional AE summaries by SOC, PT, and maximum severity, as well as AE summaries by SOC, PT, and relationship to study procedure will be provided. Serious AEs will also be summarized by SOC and PT.

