For acute success rate at 0.5h post CPVI, the number of subjects who achieved this endpoint and its percentage will be presented. A two-sided binomial exact 95% confidence interval will be computed.

For CF and Force Time Integral for index procedure by PV segments, descriptive summary statistics and the 95% two-sided asymptotic confidence intervals will be presented.

For PV reconnections after the index procedure, descriptive summary statistics will be presented. Frequency counts and percentages will be used to summarize the sites of PV reconnection. A two-sided binomial exact 95% confidence interval will be computed. Proportion of PV reconnections will be computed for each subject. And then the descriptive summary statistics and 95% two-sided asymptotic confidence intervals will be used to summarize the proportion of PV reconnection across subjects.

For total procedural, ablation time and fluoroscopy time, descriptive summary statistics and 95% two-sided asymptotic confidence intervals will be presented.

Study No.: BW-201501

Statistical analysis plan

Version: 2.0

Version date: May 19, 2016

Confidential

Correlation between the secondary efficacy endpoints and the primary efficacy endpoint will be explored with appropriate statistical methods (such as regression analysis or correlation coefficient and so on).

Safety endpoint:

The incidence of AEs related with the procedure and study catheter.

Revision date: May 19, 2016

Document Final 2.0

version:

Study No.: BW-201501

Statistical analysis plan

Version: 2.0

Version date: May 19, 2016

Confidential

Signature Page

Title: The Effectiveness and Safety in the treatment of CPVI for Symptomatic Paroxysmal Atrial Fibrillation with THERMOCOOL® SMARTTOUCH™ Catheter in China——A Multi-center Clinical Registry Study

Study No.: BW-201501

Sponsor: JJMS

Prepared by:

Redacted

Reviewed by:

Redacted

Table of Contents

1 Project introduction	8
1.1 Background	8
1.2 Rationale	9
1.3 Device Description.....	10
1.4 Risk analysis.....	10
1.4.1 Description of Risk Analysis	11
1.4.2 Minimization of Risks	13
1.4.3 Precautions.....	13
1.4.4 Potential Benefit	13
2 Study Objective	14
3 Study Design.....	14
3.1 Screening.....	14
3.2 Informed Consent Form (ICF).....	14
3.3 Number of Centers	14
3.4 Subject Selection - Inclusion Criteria.....	15
3.5 Subject Selection - Exclusion Criteria.....	15
3.6 Subject Disposition	17
3.7 Study Process.....	18
4 Study Endpoint	19
4.1 Primary Efficacy Endpoint.....	19

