6.3.3 Demographic and Baseline Characteristics

The patients' demographic characteristics (age, gender and nationality) are summarized and described. The qualitative indicators are summarized with frequency and percentage, and the quantitative indicators are summarized with descriptive statistics (mean, standard deviation, median, maximum and minimum, Q1 and Q3). The demographic and baseline characteristics need present for all enrolled subjects and ITT population.

The baseline characteristics shown below are analyzed with the descriptive method similar to that used for demographic characteristics:

1) History of fibrillation atrial, including:

- Symptomatic fibrillation atrial history (month) according to the initial PAF symptom or record
- Average duration (hour) per episode within 12 months before enrollment
- Average frequency of episodes (times/month)
- Objective evidence of confirmed fibrillation atrial within 12 months before enrollment: surface electrocardiogram (ECG), 24-hour dynamic electrocardiogram (24 Holter), transtelephonic monitor (TTM) and others
- Presence of fibrillation atrial related symptom
- Fibrillation atrial/ Atrioventricular tachycardia/ auricular flutter (AF/AT/AFL status)
- Paroxysmal or persistent fibrillation atrial related symptom

2) Medical history – underlying heart disease, including:

- Presence of definite organic heart disease
- Type of organic heart disease

- Cardiac function NYHA grading
- Presence of other complications
- Type of other complications
- Presence of thrombotic disease history
- Type of thrombotic disease history
- Presence of hemorrhagic disease
- Presence of diabetes
- Presence of other arrhythmia symptoms
- Type of other arrhythmia disease

3) Echocardiography

- Whether the subject has undergone transesophageal echocardiography (TEE) examination within 24 hours before the procedure
- Presence of atrial thrombosis
- Whether the left atrial diameter has been tested?
- Left atrial diameter (LAD) (cm)
- Whether the subject has undergone trans thoracic echocardiography (TTE) examination?
- Whether the ultrasound cardiography shows left ventricular ejection fraction
- Left ventricular ejection fraction (LVEF) (%) showed with echocardiography

4) Treatment of fibrillation atrial and other heart diseases, including:

- Whether the subject has taken antiarrhythmic drugs within the past 3 months
- Whether the drug has been stopped for 5 half-lives

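### SAP 6.5.1 states the stepwise removal rule backwards: factors enter the multivariable logistic model at p<0.2 and are then removed at p<0.2

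*SAP*

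**What the plan says.** The stated aim in SAP 6.5.1 is: "Logistic regression method will be used to analyze the effect of baseline variables and procedure parameters on the primary effectiveness endpoint". Selection has two stages, set out in one sentence.

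- Stage 1, univariate screen: "the influence factor with p-value <0.2 will be placed into multiple factor regression model for further analysis".
- Stage 2, within the multivariable model: "step-wise regression method will be used for further variable screening", and then "of which, the influence factor with p-value <0.2 will be removed from multiple factor model".

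Protocol 8.4.2 and the SAP synopsis mention only exploratory logistic regression and give no threshold. SAP 6.1 sets a general two-sided 0.05 level unless something else is specified. SAP sections 8 (changes to planned methods) and 9 (data processing) contain no entries. SAP section 10 leaves programming specifications to a separate document.

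**The concern.** Both stages use the same inequality in the same direction. A factor earns its place with a small p-value and loses it for the same reason. The final model would then hold the factors that show the least association after adjustment, the opposite of what the analysis is for.

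Contact force is tested separately against the primary endpoint (SAP 6.5.3), and both documents plan to relate the secondary efficacy endpoints to it (protocol 8.4.3: "Correlation between the secondary efficacy endpoints and the primary efficacy endpoint will be explored"; the SAP synopsis repeats this). The other factors have no such back-up. For baseline items SAP 6.3.3 says "The baseline characteristics shown below are analyzed with the descriptive method similar to that used for demographic characteristics", and for procedure items SAP 6.4 says "Descriptive analysis is conducted for ablation procedure parameters, and the procedure parameters include". For these, the logistic model and its univariate screen are the only planned analysis against recurrence.

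**Working it through.** **Step 1. The rule, case by case.** The inputs are the two thresholds in SAP 6.5.1, both p<0.2.

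| Univariate p | Adjusted p | Written rule | Reversed rule (remove p≥0.2) |
|---|---|---|---|
| ≥0.2 | – | never enters | never enters |
| <0.2 | <0.2 | enters, then removed | enters, kept |
| <0.2 | ≥0.2 | enters, kept | enters, then removed |

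The written rule keeps exactly the class that selection is meant to drop. SAP 6.5.1 does not say whether removal is repeated. If it is repeated until nothing qualifies, the final model is empty or holds only factors with adjusted p≥0.2. If it is done once, the survivors are those with p≥0.2 in the first multivariable fit, and some may fall below 0.2 on refitting.

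**Step 2. Items listed.** SAP 6.3.3 lists 3 demographic items and 7+11+7+5+5+1+2 = 38 baseline items. SAP 6.4 lists 23 procedure items. Four of these are also secondary efficacy endpoints (immediate success; contact force; reconnection targets; procedural, ablation and fluoroscopy times), leaving 23−4 = 19.

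**Step 3. Illustration of size.** From the documents: 188 subjects (planned minimum) and 65% success. Assumed, not in the documents: 10 candidates, 2 of them true predictors; odds ratio 1.3, 1.5 or 1.8 per SD; pairwise correlation 0, 0.3 or 0.6. Each of 1,000 runs per scenario applied the univariate screen at p<0.2, then backward removal without re-entry, which is one reading of stepwise. Percentage of true predictors kept:

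| Odds ratio | Correlation | Written, repeated | Written, one pass | Reversed |
|---|---|---|---|---|
| 1.3 | 0 | 0.4 | 3.3 | 63 |
| 1.3 | 0.3 | 21 | 35 | 53 |
| 1.3 | 0.6 | 48 | 56 | 41 |
| 1.5 | 0 | 0.2 | 2.0 | 87 |
| 1.5 | 0.3 | 9.8 | 23 | 81 |
| 1.5 | 0.6 | 23 | 38 | 66 |
| 1.8 | 0 | 0.0 | 0.2 | 98 |
| 1.8 | 0.3 | 1.2 | 5.2 | 96 |
| 1.8 | 0.6 | 6.0 | 17 | 86 |

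The written rule keeps fewer true predictors in 8 of the 9 scenarios, under either reading. In the exception (odds ratio 1.3, correlation 0.6) it also keeps 61-65% of null factors, against 14% under the reversed rule. Correlation raises adjusted p-values, so more factors of every kind escape removal. Across all scenarios, null factors are kept in 0.3-61% (repeated), 3.4-79% (one pass) and 8.9-22% (reversed). After one-pass removal, the refitted model still held a factor with p<0.2 in 27-86% of runs.

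**Step 4. Cross-check.** A separate run with 10 independent candidates, log odds ratios of 0.3 and 0.6 per SD and 600 replicates gave the same picture. Under repeated removal, true predictors were kept in 0.5% and 0.2% of replicates, and the final model was empty in 98% and 99%. With the inequality reversed, they were kept in 71% and 98%.

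**The case against.** The strongest reply is that this is an evident slip. The sentence names a standard method and screens in at p<0.2, and any standard stepwise procedure removes factors that fail the stay level. SAP 6.1 specifies SAS, where the literal rule would need special code. The only level in the sentence is 0.2, so the intended rule is probably removal at p≥0.2. A slip is indeed the likeliest explanation. But the SAP is the record of what was planned, and 0.05 (the general level in 6.1) or another stay level cannot be ruled out. A silent correction in code would be an undocumented analyst's choice.

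The second reply is that little is at stake. This stands in part. The analysis is exploratory, the univariate results can still be reported, and the primary decision does not depend on it.

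The third is that the item counts overstate the exposure, which is fair. SAP 6.5.1 refers the reader only to 6.3.3 and never names the 6.4 list as the candidate set. Several items merely record whether a test was done. Others should be nearly constant given the eligibility criteria or the required procedure. The counts are therefore an upper limit on the usable candidates.

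The fourth is that the simulation rests on assumed inputs and excludes re-entry, and that p<0.2 is weak evidence, since about one null factor in five meets it by chance. All of this is true. It limits what the percentages can be used for, but not the direction of the error.

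**Conclusion.** The concern holds. As written, SAP 6.5.1 removes the factors that the model is meant to identify, and nothing in the protocol or SAP corrects it. That conclusion needs no assumption beyond the text. The size depends on the assumed candidates, effects and correlation: true predictors are kept in 0-48% of runs with repeated removal and 0.2-56% with one pass, against 41-98% with the clause reversed. The ranges overlap because of the weak-effect, high-correlation scenarios. The consequence is limited to an exploratory analysis, and whether the code follows the written rule cannot be told from the available documents. It should be corrected, but it does not threaten the trial's main conclusion.

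**What to change.** In SAP 6.5.1, give the entry and stay levels explicitly and reverse the removal clause, so that a factor whose adjusted p-value is at or above the stay level is removed. If 0.2 is the intended stay level, the clause becomes removal at p≥0.2; otherwise give the intended level. It would also help, though it is secondary, to say whether removal is repeated and whether a removed factor may re-enter. Check the separate programming specifications (SAP section 10) against the corrected sentence before database lock.

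The cost is one sentence and one check. Sample size, data collection and the primary test do not change.
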